## 2 Changes

### 2.1 Section 1 Summary

#### Primary objective

To confirm *the effect efficacy* in terms of glycaemic control of treatment with mealtime faster-acting insulin aspart in combination with insulin degludec in adults with Type 1 Diabetes Mellitus.

#### Secondary objectives

To confirm *the effect efficacy* in terms of glycaemic control of treatment with postmeal faster-acting insulin aspart in combination with insulin degludec in adults with Type 1 Diabetes Mellitus.

To confirm superiority of mealtime faster-acting insulin aspart compared to mealtime NovoRapid® both in combination with insulin degludec in adults with Type 1 Diabetes Mellitus in terms of:

- Postprandial glucose regulation (meal test)
- ~~Postprandial glucose excursions (1,5-anhydroglucitol)~~ Overall glycaemic control ( $HbA_{1c}$ )
- ~~Overall glycaemic control ( $HbA_{1c}$ )~~ Postprandial glucose excursions (1,5-anhydroglucitol)

To compare other efficacy and safety endpoints across mealtime faster-acting insulin aspart, postmeal faster-acting insulin aspart and mealtime NovoRapid®, all in combination with insulin degludec in adults with Type 1 Diabetes Mellitus.

#### Primary endpoint

Change from baseline in  $HbA_{1c}$  ~~after 26 weeks of treatment after randomisation~~

#### Key secondary endpoints

Confirmatory secondary endpoints

- Change from baseline in 1-hour post prandial glucose increment ~~after 26 weeks of treatment after randomisation~~ (meal test)
- Change from baseline in 1,5-anhydroglucitol ~~after 26 weeks of treatment after randomisation~~

#### Key exclusion criteria:

1. Within the past 180 days any of the following: myocardial infarction, stroke or hospitalization for unstable angina and/or transient ischemic attack
2. Subjects presently classified as being in New York Heart Association (NYHA) Class IV
3. Currently planned coronary, carotid or peripheral artery revascularisation

3. 4. Diabetic ketoacidosis requiring hospitalisation within the last 180 days prior to screening (Visit 1)

4. 5. Treatment with any medication for the indication of diabetes or obesity other than stated in the inclusion criteria in a period of three months before screening (Visit 1)

## 2.2 Section 2 Flowchart

Trial Periods	Protocol section	Screening	8 week run-in period							Randomisation	26 week treatment period																Follow-up 1	Follow-up 2	Premature Discontinuation
			V1	V2	P3 P4	V5	P6 P7 P8	V9	V10		V11	P12 P13	V14	P15 P16 P17	V18	P19 P20 P21	V22	P23 P24 P25	V26	P27 P28 P29	V30	P31 P32 P33	V34	P35	V36	V37	P38	V36A	
Visit (V) Phone contact (P)	8.1.7 8.1.8																												
Timing of visit (weeks)		-10	-8	-7 -6	-5	-4 -3 -2	-1	0	1	2 3	4	5 6 7	8	9 10 11	12	13 14 15	16	17 18 19	20	21 22 23	24	25	26	7 days	30 days				
Visit window (days)		+10	±3	±3	±3	±3	±3	0	±3	±3	±3	±3	±3	±3	±3	±3	±3	±3	±3	±3	±3	±3	±3	±3	+5	+5			
glucose																													
4-point profile	8.3.2.1			x	x	x	x	x	x	x	x	x	x	x	x	x	x	x	x	x	x	x	x	x	x	x	x		
7-9-7-point profile	8.3.2.2								x							x									x		x		
9-point profile	8.3.2.2	-	-	-	-	-	-	*	-	-	-	-	-	*	-	-	-	-	-	-	-	-	*	-	-	*			
Glucose metabolism																													
1,5-anhydroglucitol	8.5.1.1							x			x		x		x		x		x		x		x		x		x		
Fasting plasma glucose	8.5.1.2							x							x						*		x		x		x		
HbA 1c	8.5.1.3	x			x		x	x		x		x		x		x		x		x		x		x		x			
Lipids	8.5.1.4	x						x							x									x		x			
SAFETY																													
Adverse events	12		x	x	x	x	x	x	x	x	x	x	x	x	x	x	x	x	x	x	x	x	x	x	x	x			
Hypoglycaemic episodes	8.4.1.1		x	x	x	x	x	x	x	x	x	x	x	x	x	x	x	x	x	x	x	x	x	x	x	x			
Injection site reaction	8.4.1.2	x	x	x	x	x	x	x	x	x	x	x	x	x	x	x	x	x	x	x	x	x	x	x	x	x			
Technical complaints	12.4	x	x	x	x	x	x	x	x	x	x	x	x	x	x	x	x	x	x	x	x	x	x	x	x	x			
Body measurements																													
Height	8.4.4	x																											
Weight	8.4.4	x							x						x						x			x		x		x	
Physical examination	8.4.5	x							x						x			x					x		x		x		
Vital signs	8.4.6	x							x						x			x					x		x		x		
Eye examination	8.4.2	x							x						x			x					x		x		x		
ECG	8.4.3	x							x						x			x					x		x		x		

## **2.3 Section 3.5 Insulin degludec**

At the time of this protocol issuance, insulin degludec is approved in more than 60 countries including US, all EU countries and Japan.

## **2.4 Section 4 Objectives and endpoints**

### **2.4.1 Section 4.1 Objectives**

#### **2.4.1.1 Section 4.1.1 Primary objective**

To confirm *the effect efficacy* in terms of glycaemic control of treatment with mealtime faster-acting insulin aspart in combination with insulin degludec in adults with Type 1 Diabetes Mellitus.

#### **2.4.1.2 Section 4.1.2 Secondary objectives**

To confirm *the effect efficacy* in terms of glycaemic control of treatment with postmeal faster-acting insulin aspart in combination with insulin degludec in adults with Type 1 Diabetes Mellitus.

To confirm superiority of mealtime faster-acting insulin aspart compared to mealtime NovoRapid® both in combination with insulin degludec in adults with Type 1 Diabetes Mellitus in terms of:

- Postprandial glucose regulation (meal test)
- ~~Postprandial glucose excursions (1,5-anhydroglucitol)~~ Overall glycaemic control ( $HbA_{1c}$ )
- ~~Overall glycaemic control ( $HbA_{1c}$ )~~ Postprandial glucose excursions (1,5-anhydroglucitol)

To compare other efficacy and safety endpoints across mealtime faster-acting insulin aspart, postmeal faster-acting insulin aspart and mealtime NovoRapid®, all in combination with insulin degludec in adults with Type 1 Diabetes Mellitus.

### **2.4.2 Section 4.2 Endpoints**

- Baseline is defined as randomisation (Visit 10).

#### **2.4.2.1 Section 4.2.1 Primary endpoint**

- Change from baseline in  $HbA_{1c}$  ~~after 26 weeks of treatment after randomisation~~

#### **2.4.2.2 Section 4.2.2 Secondary endpoints**

##### **2.4.2.3 Section 4.2.2.1 Confirmatory secondary endpoints**

- Change from baseline in 1-hour post prandial glucose increment ~~after 26 weeks of treatment after randomisation~~ (meal test)
- Change from baseline in 1,5-anhydroglucitol ~~after 26 weeks of treatment after randomisation~~

#### 2.4.2.4 Section 4.2.2.2 supportive secondary endpoints

##### Supportive secondary efficacy endpoints

*26 weeks after randomisation*

- Change from baseline in fasting plasma glucose ~~after 26 weeks of treatment~~
- Percentage of subjects reaching HbA1c targets
  - ~~HbA1c responder after 26 weeks of treatment:~~
    - HbA1c < 7.0%
    - HbA1c < 7.0% without severe hypoglycaemia
    - HbA1c < 7.0% without severe hypoglycaemia and minimal weight gain (<3.0%)
- Change from baseline in 30- min, 1- hour, 2- hour, 3- hour and 4- hour PPG and 30- min, 2- hour, 3- hour and 4- hour PPG increment ~~after 26 weeks of treatment~~ (meal test)
- Change from baseline in 7-9-7-point self-measured plasma glucose ~~assessed by after 26 weeks of treatment:~~
  - Mean of the 7-9-7-point profile
  - Post prandial glucose and post prandial glucose increment (mean, breakfast, lunch, main evening meal)
  - Fluctuation in 7- 9-7-point profile
  - Change in the nocturnal self-measured plasma glucose measurements
- *Percentage of subjects reaching post prandial glucose target responders* (overall mean of daily post prandial glucose measurements in 7-9-7-point self-measured plasma glucose ) ~~after 26 weeks of treatment:~~
  - Overall post prandial glucose (1 hour) ≤ 7.8 mmol/L [140 mg/dL]
  - Overall post prandial glucose (1 hour) ≤ 7.8 mmol/L [140 mg/dL] without severe hypoglycaemia
  - Overall post prandial glucose (1 hour) ≤ 7.8 mmol/L [140 mg/dL] and HbA1c < 7.0% and minimal weight gain (<3.0%) without severe hypoglycaemia
- ~~Insulin dose (basal insulin dose, total and individual meal insulin dose) after 26 weeks of treatment.~~
  - Change from baseline in lipids-lipoproteins profile ~~after 26 weeks of treatment~~ (total cholesterol, high density lipoproteins, low density lipoproteins)
  - Insulin dose (basal insulin dose, total and individual meal insulin dose).

##### Supportive secondary safety endpoints

- Number of *treatment emergent* adverse events *during the 26 weeks after randomisation*~~during 26 weeks of treatment~~
- Number of *treatment emergent* injection site reactions *during the 26 weeks after randomisation*~~during 26 weeks of treatment~~

- Number of hypoglycaemic episodes classified both according to the American Diabetes Association definition and Novo Nordisk definition *during the 26 weeks after randomisation during 26 weeks of treatment*
  - Overall
  - Daytime and nocturnal hypoglycaemic episodes (00:01-05:59 – inclusive)
  - Hypoglycaemic episodes from start of meal until 1, 2, 4 hours and from 2 hours (exclusive) to 4 hours (inclusive) after start of meal
- Change from baseline *26 weeks after randomisation after 26 weeks of treatment* in clinical evaluations:
  - Physical examination
  - Vital signs
  - Electrocardiogram
  - Fundoscopy/fundus photography
- Change from baseline *26 weeks after randomisation after 26 weeks of treatment* in central laboratory assessments:
  - Haematology
  - Biochemistry
  - Urinalysis
- *Change from baseline in anti-insulin aspart (specific and cross-reacting with human insulin) antibody development*
- ~~Total insulin aspart antibodies (amount of antibodies specific for insulin aspart and cross-reacting with human insulin)~~
- Change from baseline *after 26 weeks of treatment* in weight and body mass index

## **2.5 Section 5.2.1 Rationale for choice of non-inferiority margin**

Placebo controlled trials will usually be considered unethical to conduct in a T1DM diabetic population and it can therefore be difficult to assess the true NovoRapid® effect. In a recently finalised faster-acting insulin aspart trial (NN1218-4049) in a bolus insulin naïve T2DM adult population comparing a basal insulin treatment in addition to metformin to a full basal bolus insulin treatment in addition to metformin the estimated treatment difference in change from baseline HbA1c was - 0.94%-point [-1.17; -0.72] (data on file). In this trial the addition of 3 times daily faster-acting insulin aspart lead to a reduction in HbA1c of 1.16%-point after 18 weeks of treatment. In a similar phase 4 trial (ref. 1) investigating the stepwise addition of NovoRapid® to a full basal bolus regimen in bolus naïve T2DM adults the observed reduction in HbA1c after 21 weeks of treatment was 1.15%-point (data on file) with 3 times daily NovoRapid® added to basal insulin. This gives some indication that the effect of NovoRapid® versus placebo would be close to the 0.94%-point observed in trial NN1218-4049. Using a non-inferiority margin of 0.4%, one of the suggested margins in the FDA guidance (Ref. 2), an improvement of approximately 0.54% would have been preserved using the 0.4% non-inferiority margin. It is also worthwhile to state that the T1DM population would not have any endogenous insulin production and the true effect of NovoRapid® should be comparable to what is seen in a T2DM population.

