### Estimands

The primary objective, confirming the *efficacy effect* of treatment with mealtime faster-acting insulin aspart *compared to NovoRapid® both in combination with insulin degludec in adults with*

type 1 diabetes, will be assessed comparing by the change from baseline HbA1c to NovoRapid® using a non-inferiority approach.

*More specifically the upper limit of the 95% confidence interval should be compared to a non-inferiority margin of 0.4%. If it is below 0.4% non-inferiority will be considered confirmed and effect demonstrated.*

*The trial also aims to compare treatment arms for a number of confirmatory secondary endpoints. The family-wise type I error rate will be controlled in the strong sense using a hierarchical (fixed sequence) testing procedure. This is based on a priority ordering of the null-hypotheses, and testing them in this order using the two-sided 95% confidence interval approach until an insignificant result appears. The effect is that rejection of the null hypothesis only will be confirmed for analyses where all previous null-hypotheses have been rejected in favour of faster-acting insulin aspart.*

*The steps in the hierarchical testing procedure are:*

**Step 1 (Primary analysis):** HbA1c non-inferiority of meal-time faster-acting insulin aspart versus meal-time NovoRapid®

**Step 2:** HbA1c non-inferiority of post-meal faster-acting insulin aspart versus meal-time NovoRapid®

**Step 3:** 1-hour PPG increments superiority of meal-time faster-acting insulin aspart versus meal-time NovoRapid®

**Step 4:** HbA1c superiority of meal-time faster-acting insulin aspart versus meal-time NovoRapid®

**Step 5:** 1,5-Anhydroglucitol superiority of meal-time faster-acting insulin aspart versus meal-time NovoRapid®

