### **2.29.1      Section 17.1 Sample size calculation**

The primary objective of this trial is to confirm *the effect efficacy* of treatment with mealtime faster-acting insulin aspart in combination with insulin degludec. This is done by showing that mealtime faster-acting insulin aspart is non-inferior to mealtime NovoRapid® both in combination with insulin degludec in terms of glucose lowering effect as assessed by mean change from baseline in HbA1c ~~after 26 weeks after randomisation of treatment~~ using a non-inferiority margin of 0.4% (absolute). The non-inferiority margin of 0.4% (absolute) was chosen ~~in accordance with the FDA guidance~~ as described in section 5.2.1. The statistical evaluation will be done as described in section 17.3.

The trial also aims to confirm *efficacy the effect* of treatment with mealtime faster-acting insulin aspart and postmeal faster-acting insulin aspart, for a number of secondary confirmatory endpoints using the hierarchical testing procedure as described in section [2.29.3.1](#) 17.1. The sample size is determined to ensure a sufficient power for the first step (the primary objective: HbA1c non-inferiority of mealtime faster-acting insulin aspart) and the second step (HbA1c non-inferiority of postmeal faster-acting insulin aspart) in the hierarchical testing procedure.

*In, previous trials where faster aspart has been investigated in similar designs, the completion rates have been high. Therefore it will not be unexpected that treatment discontinuation might be as low as 8% where trial discontinuation constitutes half of these.*

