**Step 4: HbA1c superiority of meal-time faster-acting insulin aspart versus meal-time NovoRapid®**

**Step 5: 1,5-Anhydroglucitol superiority of meal-time faster-acting insulin aspart versus meal-time NovoRapid®**

### **Change from baseline in HbA1c after 26 weeks of treatment after randomisation (step 2)**

*If the primary objective is confirmed the effect of treatment with postmeal faster-acting insulin aspart in terms of glycaemic control is to be investigated by showing that postmeal faster-acting insulin aspart is non-inferior to NovoRapid® both in combination with insulin degludec in terms of glucose lowering effect as assessed by change from baseline in HbA1c 26 weeks after randomisation.*

*The non-inferiority will be evaluated based on a two-sided 95% confidence interval of mean treatment difference (postmeal faster-acting insulin aspart minus mealtime NovoRapid®) obtained from the primary statistical analysis in 1).*

~~Step 2 in the hierarchical testing procedure is to confirm efficacy of treatment with postmeal faster-acting insulin aspart in terms of glycaemic control by showing that postmeal faster-acting insulin aspart is non-inferior to NovoRapid® both in combination with insulin degludec in terms of glucose lowering effect as assessed by change from baseline in HbA1c after 26 weeks of treatment using a non-inferiority margin of 0.4%.~~

~~The non-inferiority will be evaluated as described in section 17.3 based on a two-sided 95% confidence interval of mean treatment difference (postmeal faster-acting insulin aspart minus mealtime NovoRapid®) obtained from the primary statistical analysis.~~

~~The sensitivity of the analysis will be addressed as described in section 17.3.~~

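### Does Section 5.2.1 overstate the effect preserved by the 0.4% margin by working from the point estimate alone?

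*Protocol*

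**What the plan says.** Section 5.2.1 (Amendment 2, item 2.5) argues that NovoRapid's effect over placebo cannot easily be measured in type 1 diabetes and borrows it from trials in type 2 diabetes. In a trial of faster aspart added to basal insulin and metformin, the estimated HbA1c difference is printed as "0.94%-point [-1.17; -0.72] (data on file". A second trial, in which NovoRapid was added, showed a similar fall in HbA1c (1.15 against 1.16%-point). From this the section reasons: "This gives some indication that the effect of NovoRapid® versus placebo would be close to the 0.94%-point observed in trial NN1218-4049". It notes that 0.4% is one of the margins suggested in FDA guidance and concludes that "an improvement of approximately 0.54% would have been preserved using the 0.4% non-inferiority margin". A closing sentence argues that the effect in type 1 diabetes should be comparable, since those subjects make no insulin of their own.

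Two other places connect to this. The amended Section 17.1 says the margin was chosen "as described in section 5.2.1", replacing a direct reference to the guidance. The Estimands text in Section 17 compares the upper limit of the 95% confidence interval with the margin: "If it is below 0.4% non-inferiority will be considered confirmed and effect demonstrated". Step 2 applies the same reasoning to postmeal dosing.

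**The concern.** The trial has no placebo or basal-only arm. A claim that an effect has been demonstrated therefore passes through two comparisons: faster aspart against NovoRapid in this trial, and bolus insulin against none in the historical trial. The decision rule allows for sampling error in the first, by using a confidence limit. The preserved-effect figure allows for none in the second, although the interval is printed in the same paragraph.

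If a reader takes 0.54%-point as what a pass guarantees, a result just inside the margin would be credited with more benefit than the cited data support. Step 2 is where this would bite most, because Section 17.1 expects postmeal dosing to be 0.1%-point worse than mealtime NovoRapid and so places it nearer the margin.

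**Working it through.** **Inputs.** Historical effect 0.94, limits 0.72 and 1.17, and margin 0.40, all from Section 5.2.1. The confidence level is not printed; 95% is assumed. Sample size is 333 per arm, from the amended Section 17.1. The SD is read as 1.2: the printed 1.42 appears to merge deleted and inserted digits, and 1.2 reproduces the amended powers at 333 per arm (99.0% for a difference of 0 and 89.6% for 0.1).

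**1. The plan's own figure.** Preserved effect = historical effect − margin.
- 0.94 − 0.40 = 0.54%-point, which is 0.54/0.94 = 57% of the effect. The stated figure is reproduced.

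**2. The same formula at the interval limits.**
- Limit nearest zero: 0.72 − 0.40 = 0.32%-point, or 0.32/0.72 = 44%.
- Far limit: 1.17 − 0.40 = 0.77%-point, or 0.77/1.17 = 66%.
- Gap between the stated figure and the conservative one: 0.54 − 0.32 = 0.22.

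**3. Combining the uncertainty of both trials.** Step 2 stacks one worst-case limit on another. The less strict approach combines the standard errors, for a result that only just passes.
- Historical SE = (1.17 − 0.72)/(2 × 1.96) = 0.115.
- SE in this trial = 1.2 × √(2/333) = 0.093.
- Largest observed difference that still passes = 0.40 − 1.964 × 0.093 = 0.217.
- Implied effect over basal insulin alone = 0.94 − 0.217 = 0.723.
- Combined SE = √(0.115² + 0.093²) = 0.148.
- Lower 95% limit = 0.723 − 1.96 × 0.148 = 0.433%-point.
- Gap from the stated figure: 0.54 − 0.43 = 0.11. For SD between 1.1 and 1.42 the limit runs only from 0.427 to 0.444.

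**4. Does the qualitative conclusion hold?** A pass implies some effect over basal insulin alone if the margin is smaller than the historical effect. At the limit nearest zero, 0.40 < 0.72, so it does.

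**5. Where is 0.54 used?** The power calculation uses the margin, the SD, the assumed differences and the sample size. The decision rule uses the confidence limit and 0.4%. Neither takes 0.54 as an input. The 0.4% margin was already in Section 17.1 of the protocol before Amendment 2, justified there by the FDA guidance.

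**The case for a change.** The case for a change is reasonable. The text is operative, 0.54 is the only figure offered for what the margin preserves, and Section 17.1 now points to this section for the margin. Both ways of allowing for historical uncertainty give less than 0.54. Neither covers the step from faster aspart in type 2 diabetes to NovoRapid in type 1 diabetes, which the section supports only by comparing two type 2 trials and by a general argument about endogenous insulin. One added sentence would put the more cautious figure on record before the results are known.

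What stands is that the interval is printed and not carried through. The rest carries less weight:

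- Calling the gap an overstatement compares an estimate with a confidence bound. The sentence is hedged and gives no minimum. A reader who wants one has the interval in the same paragraph and needs a single subtraction.
- The size of the gap depends on the method (0.22 or 0.11), and the protocol fixes neither a method nor a fraction to be retained, so 44% breaks no rule of its own.
- A result just inside the margin is not what the design expects, even for step 2: at the assumed difference of 0.1 the upper limit would be about 0.1 + 1.964 × 0.093 = 0.28, well short of 0.40.
- Putting 0.32 forward as assured would also claim too much, because it too rests on the carry-over from type 2 to type 1 diabetes.

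**Conclusion.** The observation is accurate, but it does not call for a change. Section 5.2.1 reports a correct, approximate preserved effect of 0.54%-point. A cautious reader would set 0.32%-point (limit nearest zero) or about 0.43%-point (combined standard errors, result just passing) beside it. Those figures assume that the historical interval is a 95% interval and that the type 2 effect carries over to NovoRapid in type 1 diabetes; the combined figure also reads the SD as 1.2, though it hardly depends on it.

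Nothing in the trial turns on which figure is shown. The margin, sample size, testing order and decision rule would all be the same, and the claim that an effect is demonstrated names no size and holds on the conservative limit. A second descriptive number could be added as a courtesy to readers, or given when the results are discussed. Leaving it out costs the trial nothing.

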## **2.5.1 Section 5.3.2 Bolus insulin titration**

In the 26 week treatment period, the Investigator should focus on optimising the bolus insulin. The bolus insulin will be titrated to the glycaemic target of ~~fasting and pre-prandial and bedtime~~ plasma glucose between 4.0-6.0 mmol/L [71 - 108 mg/dL] in a treat-to-target fashion.

## **2.6 Section 5.4 Treatment after discontinuation of trial product**

When discontinuing trial products, the subject should be switched to a suitable marketed product at the discretion of the Investigator. *Doses of subsequent antidiabetic treatment should be carefully titrated based on blood glucose measurements, considering the stable effect and long half-life of insulin degludec.*

## **2.7 Section 6.2 Inclusion criteria**

For an eligible subject, all inclusion criteria must be answered “yes”.

1. Informed consent obtained before any trial-related activities. Trial-related activities are any procedures that are carried out as part of the trial, including activities to determine suitability for the trial.
2. Male or female, age  $\geq 18$  years (for Japan and Taiwan: age  $\geq 20$  years) at the time of signing informed consent
3. Type 1 Diabetes Mellitus (based on clinical judgement and/or supported by laboratory analysis as per local guidelines)  $\geq 12$  months prior to screening
4. Currently treated with a basal-bolus insulin regimen for at least 12 months prior to screening (Visit 1)
5. Currently treated with a basal insulin analogue for at least 4 months prior to screening (Visit 1)
6. HbA1c 7.0-9.5% (53-80 mmol/mol) (both inclusive) as assessed by central laboratory
7. Body Mass Index  $\leq 35.0$  kg/m^2
8. Ability and willingness to adhere to the protocol including performing of self-measured plasma glucose profiles and meal test
9. Ability and willingness to take at least three mealtime boluses a day every day during the trial
10. Not currently using *flash glucose monitoring* or real time continuous glucose monitoring system and/or willing not to use *flash glucose monitoring* or a real time continuous glucose monitoring system during the trial

